If the actual NPV is 0.85, and if an exact binomial test is used to test the above hypotheses, a total of 89 predicted non-responders using $TUV_{global[b]}$ are needed for 90% power and a total of 71 non-responders using $TUV_{global[b]}$ are needed for 80% power.

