To evaluate the power characteristics of this process with 3 correlated readers where at least the same two of the three readers must reject both null hypotheses above, a simulation study was performed. Correlated binomial random variables were generated using a copula. The hypotheses were tested for each simulated reader using an exact binomial test, and the number of iterations where at least the same two of the three readers rejected both hypotheses was counted. Under the conditions above this procedure has power 0.93 when $\rho = 0.7$ and 0.89 when $\rho = 0.9$.

In Arm 3 of the NAV3-31 study a ratio of 5 non-responders to 1 responder was observed. If this ratio is maintained in NAV3-33 for the $\Delta TUV_{global[5w]}$ with bucketing predictions, a total of 600 patients is needed to achieve the desired power. That is, a total of 500 clinical non-responder patients is expected to be enrolled before reaching the required 100 clinical responders.

Taking into account a 10% dropout rate, the anticipated total sample size for the study is approximately 672 patients (560 clinical non-responders and 112 clinical responders). That is:

- Clinical Non-Responders: 90% completion rate relative to 560 enrolled patients will result in 500 completed patients
- Clinical Responders: 90% completion rate relative to 112 enrolled patients will result in 100 completed patients

Because there is uncertainty about how responding and non-responding patients will enroll, enrollment may continue until at least 560 clinical non-responders and 112 clinical responders are participating in the study. The cumulative enrollment of clinical non-responders and responders will be tracked throughout the study in order to stop enrollment once the required number has been reached for each clinical category. This tracking of clinical response and non-response status will be performed by individuals without knowledge of the TUV data. At the Sponsor's discretion, the week 12 clinical response outcomes may be used to help track enrollment.

If the two co-primary endpoints are achieved (i.e., both null hypotheses are rejected for at least the same 2 out of 3 readers), then the following hypotheses will be tested at one-tailed 0.025 for the key secondary endpoint of NPV of TUV_{global[b]} with respect to ACR50 at week 24:

$$H_{03}: \pi_{\text{NPV}} \le 0.7$$

 $H_{A3}: \pi_{\text{NPV}} > 0.7;$

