If the actual NPV is 0.85, and if an exact binomial test is used to test the above hypotheses, a total of 89 predicted non-responders using $TUV_{global[b]}$ are needed for 90% power and a total of 71 non-responders using $TUV_{global[b]}$ are needed for 80% power. Enrollment of predicted non-responders at baseline will be tracked in order to ensure enough subjects are enrolled to achieve at least 80% power for this endpoint.

All enrollment tracking will be done in aggregate by individuals without knowledge of the subject-level data. Enrollment tracking will include the total number of predicted non-responders at baseline, the total number of clinical responders at or beyond week 12, and the total number of clinical non-responders at or beyond week 12.

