4.2.2 Analysis of Key Secondary Efficacy Variables

NPV of TUV_{global[b]} will be calculated for each reader. The 95% exact (Clopper-Pearson) confidence intervals will be provided. Observed significance levels (p-values) for the exact binomial tests of NPV of TUV_{global[b]} greater than 0.7 will be provided.

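### Key secondary NPV test: power is tracked on a baseline count with no dropout allowance, 89 falls just short of 90% power, and no reader success rule is stated

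*SAP*

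**What the plan says.** - **Test.** SAP 1.3 opens the key secondary test only after both co-primary nulls are rejected by the same two of three readers; "then the following hypotheses will be tested at one-tailed 0.025 for the key secondary endpoint of NPV". The null is NPV of at most 0.70. Protocol 9.4 has the same gate.
- **Sizing.** SAP 1.3 sets the alternative and the method: "If the actual NPV is 0.85, and if an exact binomial test is used to test the above hypotheses". Protocol 9.4 and SAP 1.3 then give 89 predicted non-responders for 90% power and 71 for 80% (in Protocol 9.4, 89 "are needed for 90% power and a total of 71 non-responders").
- **Tracking.** SAP 1.3 adds: "Enrollment of predicted non-responders at baseline will be tracked in order to ensure enough subjects are enrolled to achieve at least 80% power". Only the 80% level is a commitment. No enrolment number is attached to it, and the text does not say whose read defines a predicted non-responder.
- **Dropout.** In the same section a 10% dropout turns 500 and 100 into 560 and 112. It is not applied to 71 or 89.
- **Analysis.** In Protocol 9.5.3.2 and SAP 4.2.2 the NPV "will be calculated for each reader. The 95% exact (Clopper-Pearson) confidence intervals will be provided", with an exact binomial p-value for each. Neither section says how many readers, or which, must reject.

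**The concern.** NPV is the share of predicted non-responders who turn out to be ACR50 non-responders at Week 24. A patient counted at baseline adds nothing to the denominator without that Week 24 outcome. The tracked count is therefore at least as large as the analysed count, and the plan's own dropout rate suggests a gap of about one patient in ten. If tracking reassured the sponsor at 71 baseline patients, the test could be run below its committed power.

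Apart from the co-primaries, this is the only hypothesis with a stated alpha and a place in the testing order. With three p-values and no rule, a split result (one reader below 0.025, two above) could be called a success or a failure after the fact. Both type I error and power depend on that choice. The plan simulates multi-reader power for the co-primaries but gives none for NPV.

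**Working it through.** **Inputs.** Null NPV 0.70, alternative 0.85, one-tailed 0.025, exact binomial test, n = 71 and 89, 10% dropout, three readers, rho 0.7 and 0.9. All are in SAP 1.3. The rho values are the plan's for the co-primary simulation; their use for NPV is an assumption.

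**1. The plan's figures.** Take the smallest r with P(X ≥ r | n, 0.70) ≤ 0.025. Power is P(X ≥ r | n, 0.85).

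| n | r | actual alpha | power |
|---|---|---|---|
| 64 | 53 | 0.0145 | 0.754 |
| 70 | 57 | 0.0217 | 0.843 |
| 71 | 58 | 0.0183 | 0.830 |
| 80 | 65 | 0.0161 | 0.863 |
| 89 | 72 | 0.0140 | 0.888 |
| 90 | 72 | 0.0223 | 0.926 |

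So 71 meets 80% and 89 misses 90% by 1.2 points. Power is a sawtooth in n; it stays at or above 80% from n = 70 and at or above 90% from n = 90.

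The stated pair matches a normal approximation with continuity correction. Uncorrected, n = [(1.96·√0.21 + z·√0.1275)/0.15]², with z = 0.842 or 1.282, gives 63.9 and 81.7. Multiplying by ¼·[1 + √(1 + 2/(0.15n))]² gives 70.4 and 88.2, which round up to 71 and 89.

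**2. Dropout.** 71 × 0.9 = 63.9, so 64 remain and power is 0.754. 89 × 0.9 = 80.1, so 80 remain and power is 0.863. Averaging over a random number of dropouts (binomial, 10%) gives 0.773 and 0.869. In reverse, 71/0.9 = 78.9, so 79 at baseline for 80%; 90/0.9 = 100 at baseline for 90%. With random dropout these targets give average power 0.819 and 0.909.

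**3. Readers.** Each reader's count is binomial. The three are joined by a Gaussian copula with common correlation rho, and all have the same n and the same true NPV. The plan does not name its copula, so Gaussian is an assumption.

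Type I error, all readers at 0.70:

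| n | rho | any reader | two of three |
|---|---|---|---|
| 71 | 0.7 | 0.041 | 0.011 |
| 71 | 0.9 | 0.031 | 0.016 |
| 89 | 0.7 | 0.032 | 0.008 |
| 89 | 0.9 | 0.024 | 0.012 |
| 90 | 0.7 | 0.049 | 0.014 |
| 90 | 0.9 | 0.038 | 0.019 |

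Power at 0.85:

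| n | rho | any reader | two of three | all three |
|---|---|---|---|---|
| 64 | 0.7 | 0.89 | 0.77 | 0.60 |
| 64 | 0.9 | 0.84 | 0.76 | 0.67 |
| 71 | 0.7 | 0.94 | 0.85 | 0.70 |
| 71 | 0.9 | 0.89 | 0.84 | 0.76 |

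Two of three holds the level and, at 71 evaluable patients, keeps power above 80%. At 64 it does not.

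**The case against.** - **Nothing says enrolment stops at 71.** This stands. Enrolment is driven by clinical responder and non-responder counts, with about 672 patients anticipated, of which 71 is 10.6%. The tracking sentence commits to a power, not a number. But the stated range of evaluable patients starts at 198, where 71 is 36%, and the share with baseline TUV_global below 5 is not given. Sufficiency can be neither assumed nor ruled out.
- **Not every dropout leaves the denominator.** This stands in part. SAP 2.3 classes patients who stop anti-TNFα therapy for non-response as clinical non-responders, and its secondary rule imputes other missing Week 24 status. If those rules apply to NPV, the loss is below 10%. The table is written for the primary endpoints, so its use here is not settled.
- **The two-of-three standard is implied.** It is the natural reading, since it appears in the sentence that introduces the NPV hypothesis. There, however, it only opens the gate.
- **The 89 is trivial.** It is small, and 90% power is not promised. It is still a stated figure that the named test does not support.

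A reader might go further and infer that the plan fails to hold 0.025 and fails to deliver its power. The documents do not support that. The level is undetermined: it can be exceeded only under an any-reader rule, which neither document states, and even that rule gives 0.024 at n = 89 with rho 0.9. The two failures also do not go together: an any-reader rule keeps power at 0.84 to 0.89 with 64 evaluable patients.

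**Conclusion.** The concern holds in three limited parts.

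- **Tracked count.** The quantity tracked for power is not the quantity analysed. If the target is exactly 71 at baseline and 10% have no usable Week 24 outcome, single-reader power is 0.754 against a commitment of at least 80%. Actual power cannot be computed from the documents.
- **Stated figures.** 89 gives 88.8% power under the exact test, not 90%. 71 gives 83.0% and is adequate for 80% if all are evaluable.
- **Reader rule.** Without one, type I error is not assured. At n = 71 an any-reader rule gives 0.031 to 0.041 and at n = 89 it gives 0.024 to 0.032 (rho 0.9 to 0.7), against at most 0.016 under two of three.

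The reader figures rest on a Gaussian copula, a common n and all readers at the null. Baseline TUV_global uses reader-specific limits, so the number of predicted non-responders can differ between readers.

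**What to change.** - **SAP 1.3, tracking.** Count predicted non-responders who have an evaluable Week 24 outcome, and say whose read is counted. Otherwise state baseline targets of about 79 (80% power) and 100 (90% power). Say whether the SAP 2.3 missing-data rules apply to NPV.
- **Protocol 9.4 (and the synopsis) and SAP 1.3, figures.** Replace 89 for 90% power by 90, or keep 89 and state 88.8%.
- **Protocol 9.5.3.2 and SAP 4.2.2, reader rule.** State that the NPV null is rejected only if at least two of the three readers reject. Report the power of that rule: at n = 71, about 0.85 at rho 0.7 and 0.84 at rho 0.9.
- **Do not add a same-pair condition** (the readers who met the co-primaries must also reject here) unless its lower power is stated. If exactly two readers met the co-primaries, both must reject, and power at n = 70 is about 0.77 at rho 0.7. If all three did, the pair is undefined. Plain two of three already holds the level in the cases shown.

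The cost is wording and slightly less favourable stated figures. No extra patients are needed unless the evaluable count falls short. The change should be made before reader results are linked to Week 24 outcomes.

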2.0 Data Analysis Considerations

2.1 Types of Analyses

Efficacy, safety, and descriptive analyses will be performed on the data collected in this trial.

2.2 Analysis Populations

The following analysis populations will be defined.

Safety population – The safety population includes all patients that have been enrolled in the study and injected with at least one dose of Tc 99m tilmanocept.

Intent-to-diagnose (ITD) population – Patients in the safety population meeting the following criteria are members of the ITD population:

- were injected with Tc 99m tilmanocept at Visit 2 (Day 0)
- received planar imaging of the hands at Visit 2 (Day 0)

This population will include all patients for whom a prediction might be made, although some patients may be excluded from analysis under this definition if a prediction cannot be made due to missing imaging or clinical data.

Per-protocol (PP) population – The PP population will include all ITD patients without major protocol violations. All protocol deviations will be classified as major or minor prior to database lock.

All efficacy analyses will be carried out on the ITD and PP populations with the ITD population being the primary analysis set. All analyses of safety data and baseline patient characteristics will be carried out on the safety population. A data listing displaying the patients excluded from each population will be created, as shown in Appendix B.

2.2.1 Subgroup Definitions and Considerations

Summaries of the agreement between the primary TUV prediction algorithm and all clinical outcomes will be performed in the following subgroups:

- Age (< 60 years, 60 years and older)
- Sex
- Race (white, non-white)
- Time from RA diagnosis (< 5 years, 5 years and longer)
- Disease severity at baseline (moderate, severe)
- Previous use of biologics (yes, no)
- Previous and current use of DMARDs (background methotrexate only, other conventional DMARDs only, combination of methotrexate and other conventional DMARDs)
- Specific anti-TNF α therapy taken during trial
- Prednisone use on-study (on a stable dose, no prednisone use)
- ACPA level at baseline (high/low: 85 and above / < 85)

The study will make every effort to enroll enough patients in each of these subgroups so that half-widths of the 95% confidence intervals of sensitivity and specificity are less than 20%. P-values on parameter estimates will not be included.

2.3 Missing Data Conventions

In the statistical analysis of the primary efficacy endpoints of the study, missing data will be handled according to the following table of missing data scenarios:

Variable	Scenario	Primary Imputation Rule	Secondary Imputation Rule
Clinical Status at Week 24	Patient discontinued anti-TNFα therapy prior to Week 24 due to non- response to therapy	Patient classified as a clinical non- responder	N/Ă

Clinical Status at Week 24	Patient discontinued study for reasons not attributable to non-response	Clinical status set to missing	Impute mean clinical response*
TUV Prediction	Patient has TUV _{global[b]} that is ≥ 5 but is missing week 5 imaging data	Impute mean prediction**	Prediction is Y (patient has improved)
TUV Prediction	Patient is missing TUV _{global[b]}	Prediction set to missing	N/A

*Mean clinical response will be calculated as follows: calculate the proportion of unique patients whose clinical status is Y (patient is a clinical responder), randomly allocate this proportion of "Y" to the missing clinical status at week 24 values. Assign all other missing clinical status values "N" (patient is clinical non-responder).

**Mean prediction will be calculated as follows: using the patients for whom $TUV_{global[b]} \ge 5$, calculate the proportion whose TUV prediction is Y (patient has improved), randomly allocate this proportion of "Y" to the missing TUV predictions. Assign all other missing TUV predictions "N" (patient has not improved).

To assess the appropriateness of the missing data conventions for clinical status at week 24 and TUV prediction using mean imputation, tipping point analyses will be performed. Specifically, 95% confidence intervals for sensitivity and specificity will be plotted against increasing proportions of missing values imputed as "Y" to see at what point the conclusion of the study is reversed.

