2 STUDY OBJECTIVES

2.1 Primary Objectives

- To demonstrate that global tilmanocept uptake values (TUV_{global}) obtained before initiation of anti-TNFα therapy (TUV_{global[b]}) and at 5 weeks ± 1 week following change in therapy (TUV_{global[5w]}) has a specificity of greater than 80% to correctly specify a clinical non-response to therapy at 24 weeks.
- To demonstrate that TUV_{global} obtained before initiation of anti-TNF α therapy and at 5 weeks \pm 1 week following change in therapy has a sensitivity of greater than 65% to correctly classify a positive clinical response to therapy at 24 weeks.

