6 THERAPIES OTHER THAN INVESTIGATIONAL PRODUCT

6.1 Prior and Concomitant Therapy

All medications taken 30 days prior to Tc 99m tilmanocept injection through the post-injection safety follow-up must be documented and maintained at a stable dose according to the inclusion criteria. The subject's complete history of RA treatments will also be collected.

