1.0 Synopsis of Study Design/Procedures

This is a prospective, multicenter, open-label study designed to evaluate the early predictive capacity of quantitative Tc 99m tilmanocept planar imaging for downstream clinical response(s) in individuals with moderate to severe rheumatoid arthritis (RA) who are candidates for change in anti-TNF α therapy. Temporal changes (from baseline to 5-weeks) in quantitative imaging will be correlated with longitudinal changes (from baseline to 12 weeks and baseline to 24 weeks) in RA clinical assessments, with the intent of evaluating the clinical utility of Tc 99m tilmanocept for the expedited evaluation of antirheumatic treatment efficacy when compared with longitudinal assessments in clinical practice.

The study objectives are as follows:

Primary:

- To demonstrate that global tilmanocept uptake values (TUV_{global}) obtained before initiation of anti-TNFa therapy (TUV_{global[b]}) and at 5 weeks ± 1 week following change in therapy (TUV_{global[5w]}) has a specificity of greater than 80% to correctly specify a clinical nonresponse to therapy at 24 weeks.
- To demonstrate that TUV_{global} obtained before initiation of anti-TNFα therapy and at 5 weeks ± 1 week following change in therapy has a sensitivity of greater than 65% to correctly classify a positive clinical response to therapy at 24 weeks.

Key Secondary

 To evaluate the negative predictive value (NPV) of TUV_{global} obtained before initiation of anti-TNFα therapy (TUV_{global[b]}) relative to a clinical non-response to therapy at 24 weeks.

Secondary

- To evaluate the sensitivity and specificity of TUV_{global} obtained before initiation of anti-TNF α therapy and at 5 weeks ± 1 week following change in therapy relative to a positive clinical response or a non-response to therapy at 12 weeks.
- To evaluate the NPV of TUV_{global[b]} relative to a clinical non-response to therapy at 12 weeks.
- To evaluate the positive predictive value (PPV), NPV, and overall accuracy (OA) of TUV_{global} obtained before initiation of anti-TNF α therapy and at 5 weeks ± 1 week (Δ TUVglobal_[5w]) following change in therapy relative to a positive clinical response or a non-response to therapy at 12 and/or 24 weeks.
- To evaluate the qualitative assessment of Tc 99m tilmanocept imaging to predict clinical response or non-response following a change in anti-TNFα therapy.

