1.3 Sample Size

NAV3-33 is sized with respect to achieving specified goals in the co-primary endpoints of sensitivity and specificity of $\Delta TUV_{global[5w]}$ with bucketing. Sensitivity and specificity require knowledge of the patient's clinical status at Week 24, and so hypothesis testing will be performed after classification. The value of $\Delta TUV_{global[5w]}$ necessary to predict response vs. non-response and the value of $TUV_{global[5w]}$ necessary to predict response vs. non-response and the value of TUV_{global[b]} at baseline necessary to predict non-response will be determined in advance. The classification procedure occurs in two stages, following the baseline image acquisition and (possibly) following the 5 week image acquisition and calculation of $\Delta TUV_{global[5w]}$. After the baseline imaging, patients whose TUV_{global[5w]} is available, patients whose TUV_{global[b]} is ≥ 5 and D% is $\leq -10\%$ are predicted to be responders. All other patients are predicted to be non-responders. The Week 24 ACR50 will be used as the primary determination of clinical response for the reference standard

The hypotheses for the co-primary endpoints to be tested are:

$$H_{O1}: \pi_{Sp} \le 0.8$$

 $H_{A1}: \pi_{Sp} > 0.8;$

And

 $H_{02}: \pi_{Se} \le 0.65$ $H_{A2}: \pi_{Se} > 0.65.$

In the above π_{Sp} represents the true specificity of the classification procedure and π_{Se} represents the true sensitivity of the classification procedure when used to predict the outcome of the anti-TNF α bDMARD inhibitor therapy at 24 weeks. An overall two-tailed Type I error rate of 0.05 (one-tailed 0.025) was used without adjusting for multiple endpoints, as both co-primary endpoints must be achieved in order to have a successful study. If the actual specificity is 0.92 and the actual sensitivity is 0.8, and if an exact binomial test is used to test the above hypotheses, a total of 98 clinical non-responders and 100 clinical responders are needed for 90% power of the individual tests. That is, a minimum of 198 total patients is needed. This applies to a single reader.

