4.1.1.2 Clinical Assessments

ACR Response is derived through a combination of reductions from baseline in swollen or tender joint counts as well as improvement from baseline in at least 3 of the other parameters (patient assessment, physician assessment, pain scale, disability/functionality questionnaire, and acute phase reactant [ESR]). This study will evaluate the following three levels of ACR Response:

• ACR20: An ACR20 indicates that 20% improvement is observed in tender and swollen joint counts as well as 20% improvement in at least 3 of the other 5 criteria.

- ACR50: An ACR50 indicates that 50% improvement is observed in tender and swollen joint counts as well as 50% improvement in at least 3 of the other 5 criteria.
- ACR70: An ACR70 indicates that 70% improvement is observed in tender and swollen joint counts as well as 70% improvement in at least 3 of the other 5 criteria.

Each patient will be classified as a yes or a no for whether they meet each of the above ACR Response Criteria at each of the applicable post-baseline time points. Note that the above criteria are nested, such that if a patient is a yes for ACR70 at a given time point, then the patient is also a yes for ACR50 and ACR20 for that same time point.

A patient will be classified as improved on the CDAI depending on the baseline score as follows:

- If the baseline value is greater than 22, a reduction of more than 12 will be classified as improved. Otherwise, the patient is not improved.
- If the baseline value is between 10 and 22 (inclusive) a decrease of more than 6 will classified as improved. Otherwise, the patient is not improved.
- If the baseline value is less than 10, a decrease of more than 1 will be classified as improved. Otherwise the patient is not improved.

A patient will be classified as improved on the DAS28 with a score change of greater than 1.2.

A decrease of at least 0.22 in the HAQ-DI will be classified as improved. Otherwise, the patient is not improved on the HAQ-DI.

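### The plan does not say how Week 24 response is classed when RA treatment is added, increased or switched for inadequate response, so an ACR50 after add-on rescue counts as a response to the index anti-TNF

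*SAP*

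**What the plan says.** - **Objective.** Protocol 2.1 wants the imaging measure "to correctly classify a positive clinical response to therapy at 24 weeks". Protocol 7.2.2.4 makes that therapy the anti-TNFα agent started once the Visit 2 procedures are complete.
- **Reference standard.** SAP 4.1.1.2 defines ACR20/50/70 purely as improvement from baseline: "Each patient will be classified as a yes or a no for whether they meet each of the above ACR Response Criteria". Nothing there depends on other RA treatment received.
- **Treatment-change rule.** SAP 2.3 has two rows for Week 24 clinical status. One covers a patient for whom the scenario is "Patient discontinued anti-TNFα therapy prior to Week 24 due to" non-response; that patient is a clinical non-responder. The other covers leaving the study for other reasons, and sets the status to missing. The table is presented as a missing-data convention.
- **Background medication.** Protocol 6.1 states: "All medications taken 30 days prior to Tc 99m tilmanocept injection through the post-injection safety follow-up must be documented and maintained at a stable dose". Under the current schedule the last injection is at Week 5 and the follow-up call comes 5 ± 3 days later (Protocol 7.2.5). The intra-articular steroid criterion (Protocol 4.1.2, item 12) looks only at the period before Day 0.
- **Analysis set and robustness.** The primary set is ITD (SAP 2.2). The tipping-point analyses in SAP 2.3 vary imputed values only. RA medications are listed (SAP 6.5) but do not enter any efficacy definition.
- **Enrolment.** Counts of clinical responders and non-responders are tracked to decide when to stop recruiting (Protocol 9.4, SAP 1.3).

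**The concern.** Take a patient who responds inadequately to the new anti-TNF, stays on it, has a steroid or conventional DMARD added or raised after Week 5, and meets ACR50 at Week 24. Neither clinical-status row in SAP 2.3 applies, so SAP 4.1.1.2 records a responder. The Week 5 scan was taken before the treatment that may have produced the response. If the scan predicted non-response, a prediction that was right for the index agent is scored as a false negative.

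The design magnifies this. Non-responders are expected to outnumber responders 5 to 1, so a small fraction of the larger group is a sizeable fraction of the smaller one, and sensitivity is tested on the smaller one. The same patients would also be counted towards the responder target.

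There is a second, narrower uncertainty. A patient moved from the index agent to another anti-TNFα for non-response has stopped one drug but not the class. Row 1 can be read either way, and it does not say what happens if that patient has a recorded ACR50.

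**Working it through.** **Inputs from the plan**
- Null sensitivity 0.65: "has a sensitivity of greater than 65% to correctly classify a positive clinical response to therapy at 24 weeks" (SAP 1.0).
- Design values: "If the actual specificity is 0.92 and the actual sensitivity is 0.8" (SAP 1.3).
- One-sided level 0.025: "An overall two-tailed Type I error rate of 0.05 (one-tailed 0.025) was used without adjusting for multiple endpoints" (SAP 1.3).
- Sample size for one reader: "a total of 98 clinical non-responders and 100 clinical responders are needed for 90% power of the individual tests" (SAP 1.3).
- Ratio of 5 non-responders to 1 responder, that is 500 to 100 (SAP 1.3).

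**Inputs that are assumptions**
- c: share of non-responders to the index agent who are rescued and then reach ACR50. Range used: 1% to 2% (5 to 10 patients of 500).
- q: share of those patients who were predicted responders. Values used: 0.08 (equal to 1 - 0.92), 0.30 and 0.50.

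**Step 1: reproduce the plan's figure.** With n = 100 and p0 = 0.65, the smallest r with P(X ≥ r) ≤ 0.025 is 75 (actual level 0.021). Power at 0.80 is P(X ≥ 75 | 100, 0.80) = 0.9125. The stated 90% is reproduced.

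**Step 2: apparent sensitivity.** The rescued share of counted responders is f = 5c / (1 + 5c).
- c = 1%: f = 0.05 / 1.05 = 0.0476
- c = 2%: f = 0.10 / 1.10 = 0.0909

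Apparent sensitivity is 0.80(1 - f) + q·f. Power is P(X ≥ 75 | 100, apparent sensitivity).

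| c | q | Apparent sensitivity | Power |
|---|---|---|---|
| 0 | - | 0.800 | 0.91 |
| 1% | 0.08 | 0.766 | 0.69 |
| 1% | 0.30 | 0.776 | 0.78 |
| 1% | 0.50 | 0.786 | 0.84 |
| 2% | 0.08 | 0.735 | 0.41 |
| 2% | 0.30 | 0.755 | 0.60 |
| 2% | 0.50 | 0.773 | 0.75 |

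These figures hold the number of counted responders at 100. If the rescued patients come on top of 100 true responders, q = 0.08 gives 0.69 with 5 and 0.44 with 10, so the picture is much the same.

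**Step 3: how many patients reverse an expected result.** An observed 80/100 has p = 0.0008. Adding patients who are all false negatives:
- 7 added: 80/107 = 0.748, p = 0.020, still passes.
- 8 added: 80/108 = 0.741, p = 0.028, fails. Eight is 8/500 = 1.6% of the expected non-responders.

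**Step 4: the two-of-three-reader rule.** A simulation with 500 non-responders, 100 counted responders, q = 0.08 and a patient-level Gaussian copula (ρ = 0.7 / 0.9) gives success probability 0.95 / 0.93 with no rescued patients, 0.72 / 0.71 with 5 and 0.47 / 0.48 with 8. The plan does not describe its copula, so this shows only that requiring two readers does not protect against the effect.

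**Step 5: specificity.** With q = 0.08, removing the rescued patients from the non-responder group leaves specificity at 0.92. The effect falls on sensitivity.

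**The case against.** **The bias is conservative.** It costs the sponsor power and does not manufacture a claim. This stands when q is below the true sensitivity. It is the main reason not to rank the point higher.

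**The size rests on two figures that the documents do not give.** This stands. The rate c is not a rescue rate but a rate of rescue followed by ACR50. Patients kept on the anti-TNF with an add-on may be partial responders whose uptake fell, so q could be well above 0.08. A rescued patient predicted to respond becomes a true positive. The results for q = 0.08 are the pessimistic end.

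**Other text gives partial cover.** The prednisone subgroup (SAP 2.2.1) has categories only for a stable dose and for no use, which suggests that stable steroids were expected. Patients injected at Weeks 12 and 24 before Amendment 4 have a later safety follow-up, so for them the stable-dose window may run longer. A breach could remove a patient from the PP set if classed as major. None of this changes the classification of an observed ACR50 in the ITD analysis.

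**Stronger readings to avoid.** A reader might infer that a switch to a second anti-TNF is simply uncovered. It is ambiguous: read with the objective, row 1 can cover stopping the index agent for non-response. A reader might also infer that a handful of rescued patients would defeat the co-primary. With q = 0.08 and 100 counted responders, one to three cost about 3 to 11 points of power, and an observed 80/100 survives 7 added false negatives. Finally, stopping for intolerance is not failure through inadequate response, so it belongs in a sensitivity analysis and not in the primary rule.

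**Conclusion.** The gap is real for add-on treatment. Followed as written, the plan counts an ACR50 reached after such treatment as a response to the index agent, and no planned sensitivity analysis reclassifies it. For a within-class switch the plan is unclear, both on what the discontinued therapy refers to and on whether the row overrides a recorded ACR50.

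Under the assumed 1-2% of 500 non-responders, single-reader power for sensitivity falls from 0.91 to 0.69-0.41 (q = 0.08), 0.78-0.60 (q = 0.30) or 0.84-0.75 (q = 0.50), and an expected 80/100 reverses with about 8 added false negatives. The direction depends on most of these patients having been predicted non-responders; the inflation of the responder count does not. The documents do not show that the rate will be this high, so the point is one that should be fixed and not one that invalidates the design.

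**What to change.** 1. In SAP 2.3 row 1, state that the therapy is the index anti-TNFα agent started after Visit 2, that replacement by another anti-TNFα because of non-response is included, and that the row applies whether or not a Week 24 ACR50 was recorded.
2. Extend the same non-responder classification to RA treatment added or increased before Week 24 because of inadequate response. Use a list of qualifying changes that the sponsor fixes before database lock and without knowledge of TUV data. Without such a list, a minor or brief change could recode a genuine responder.
3. Add a sensitivity analysis that applies the classification to any such change for any reason, and report the number of patients affected by predicted class.
4. Reconcile Protocol 6.1, 7.2.6-7.2.7 and Appendix 1. The stable-dose window is unclear after Visit 5, and medication review at Visits 6 and 8 is in the text but not marked in the schedule. Data Listings 9 and 10 have no column for dose or reason for change, so confirm that both are captured.

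**Cost.** SAP wording, one table, and a check that the change and its reason are recorded. There will be slightly fewer counted responders. Some true positives may become false positives: at the design values, one such patient moves specificity from 460/500 = 0.920 to 460/501 = 0.918, and five move it to 460/505 = 0.911. This is a classification rule only and prescribes no clinical management.
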